8.5.2 Methods for Breaking the Blind

The treatment code must not be broken. However, the Investigator can unblind the patient's treatment assignment in case of medical emergency or safety concerns *if knowledge of the treatment allocation is able to improve or modify the management of the patient*. However, it is important to note that the unblinding procedure should not be used in order to assess the causality of an AE or SAE. The code may also have to be broken if someone not in the study received the IMP or if pregnancy of a randomised patient occurs. Once the decision taken, the Investigator will promptly inform the Study Safety Officer and document the reasons for the premature unblinding.

The unblinding/decoding process will be performed by the Investigator via the eCRF system. Additionally, a progress note summarising these events should be documented as part of the patient's study file, with clarification as to patient SAE outcome.

Investigators must always keep in mind that unblinding procedures will have a serious impact on the validity and analysis of the data.

**PREOB-ON3 - Clinical Study Protocol**

PREOB-ON3-CSP

V 6.1

Author: [name]

May 15, 2017

Pg. 80/81

8.6 Long-Term Pharmacovigilance System

Finally, during the course of the trial, the Sponsor plans to design, develop, and submit to the relevant CAs if needed, a detailed long-term follow-up strategy, under Pharmacovigilance Plan in line with Guideline ICH Topic E2 E.

PREOB-ON3 - Clinical Study Protocol

PREOB-ON3-CSP

V 6.1

Author: [name]

May 15, 2017

Pg. 81/82

9 PREMATURE REMOVAL FROM THE STUDY

9.1 Reasons for Early Discontinuation

Notification of patient study discontinuation (and reasons for discontinuation) will be communicated by the Investigator as soon as possible. The Investigator will document the circumstances for premature discontinuation in the patient's electronic Case Report Form as follows:

- ***Violation of eligibility criteria***

Patients will be withdrawn if incorrectly randomised (*i.e.*, not in compliance with one or more eligibility criteria). The Investigator may contact the Monitor in order to discuss the potential continuation of wrongly included patients if judged that is in the interest of the patient to continue the study.

In any case, and especially if the patient is withdrawn for safety reasons, the explanation for this discontinuation due to violation of eligibility criteria should be documented in the patient's eCRF.

- ***Adverse Events / Serious Adverse Events***

Any patients may be withdrawn from the study at the Investigator's discretion in case of a safety concern. However, patients can be withdrawn from the study for AEs or SAEs **only** if the Investigator has clearly determined that the patient's withdrawal would reduce the safety risks. In this case, the eCRF AE/SAE Form must be completed, explaining the rationale for withdrawal. In addition, the Investigator should ensure that adequate medical care and management will be provided to the patient.

- ***Withdrawn consent***

Participation in the study is strictly voluntary. A patient has the right to withdraw his/her consent from the study at any time, and for any reason, without prejudice to further treatment, care, and patient-physician relationship. Under these circumstances, an adequate standard of care will always be adopted by the Investigator. The reason(s) for withdrawing consent will also be documented in source documentation and the eCRF.

- ***Lack of patient compliance to the protocol***

- ***Study termination***

The Sponsor has the right to terminate the study at any time.

PREOB-ON3 - Clinical Study Protocol

PREOB-ON3-CSP

V 6.1

Author: [name]

May 15, 2017

Pg. 82/83

- ***Lost to follow-up***

Intensive efforts will be made to re-contact patients who do not return for scheduled visits in order to, at minimum, determine health status and the potential occurrence of AE and/or SAE. All efforts to re-contact will be documented in the source documentation and the eCRF.

- ***Reaching of endpoint***

Severe pain and/or femoral head fracture of the treated hip are the composites of the primary efficacy responder endpoint of this study. These events must carefully be documented either clinically for pain (WOMAC® VA 3.1) or radiologically for fracture (central radiologist assessment) before a patient is discontinued from the study. If severe enough to justify or warrant THA, these events will also be reported as SAE.

These events will be reported as study endpoints *via* the eCRF.

- ***Other reasons***

If no above-mentioned reasons are applicable in case of early discontinuation, the other reason(s) will be clearly documented and explained in the eCRF and source documents.

9.2 Procedure for Early Discontinuation

In case of early discontinuation and whenever possible, Investigators will ask patients to perform Visit 9 (Exit Visit) as the Premature Discontinuation Visit. At the end of the Exit visit, the Investigator will declare early discontinuation in the eCRF. However, the Investigator will continue to follow the patient (via phone calls) for the occurrence of any AEs and SAEs at Month 24, 36 and 48 post-treatment (See Table 11).

All collected data, during the visits and phone calls, should be recorded in the source documents and eCRF.

9.3 Replacement of Patients

As evaluation of the patient number to be randomised in the study took into account the percentage of discontinued patients, patients withdrawn from the study will not be replaced.

PREOB-ON3 - Clinical Study Protocol

PREOB-ON3-CSP

V 6.1

Author: [name]

May 15, 2017

Pg. 83/84

10 STATISTICAL CONSIDERATIONS AND METHODS OF ANALYSIS

A Statistical Analysis Plan (SAP) exhaustively detailing statistical methods will be generated, reviewed, approved, and signed by the biostatistician and the Sponsor, prior to database lock, at the latest. This document will be the main reference document as far as statistical analyses are concerned and therefore the description provided in this Study Protocol will not be exhaustive.

10.1 Collection and Derivation of Efficacy Assessments

10.1.1 Primary Efficacy Endpoint

Efficacy will be assessed by the following primary endpoint:

- Percentage of treatment responders at Month 24,
a treatment responder at a studied timepoint being defined as a patient who responded both:
 - Clinically, *i.e.*, if at the studied timepoint, the WOMAC® VA3.1 pain subscale score of the study treated hip improved from baseline by at least the minimal clinically important difference (MCID)^a,

and

 - Radiologically, *i.e.*, if at the studied timepoint, the study treated hip did not progress to fractural stages (ARCO III or higher), as assessed by conventional X-ray.

^aThe MCID value is set at 10 mm in accordance with the literature for WOMAC® VAS pain subscale (Ehrich *et al.*, 2000; Angst *et al.*, 2001) and with the absolute MCIDs reported in controlled, randomised, parallel group studies that evaluate treatment for hip disorders (Puopolo *et al.*, 2007; Altman *et al.*, 2007; Prior *et al.*, 2014).

For patients with a baseline WOMAC® VA3.1 pain subscale score ≥ 10 mm, the MCID can be used as a threshold value to define a clinically meaningful pain relief. These patients will be considered, at the studied timepoint, as a clinical responder if the WOMAC® VA3.1 pain subscale score of the study treated hip decreased from baseline by at least the MCID.

For patients with a baseline WOMAC® VA3.1 pain subscale score < 10 mm, the MCID cannot be used as a threshold value to define a clinically meaningful pain relief. These patients will be considered, at the studied timepoint, as a clinical responder if the WOMAC® VA3.1 pain subscale score of the study treated hip is found in the range [0; 4]. This definition is based on the literature, which states that any VAS pain rating ≤ 4 mm is labelled as “no pain” (Jensen *et al.*, 2003).

PREOB-ON3 - Clinical Study Protocol

PREOB-ON3-CSP

V 6.1

Author: [name]

May 15, 2017

Pg. 84/85

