For patients with a baseline WOMAC® VA3.1 pain subscale score < 10 mm, the MCID cannot be used as a threshold value to define a clinically meaningful pain relief. These patients will be considered, at the studied timepoint, as a clinical responder if the WOMAC® VA3.1 pain subscale score of the study treated hip is found in the range [0; 4]. This definition is based on the literature, which states that any VAS pain rating ≤ 4 mm is labelled as “no pain” (Jensen *et al.*, 2003).

Study Population

As previously described, non-traumatic osteonecrosis is generally associated with one or more risk factors. In Caucasians, it is considered that about two thirds of non-traumatic osteonecrosis are related to corticosteroid therapy and/or alcohol abuse. The remaining third includes a heterogeneous group of diseases, notably dysbaric phenomenon, haemoglobinopathies, coagulopathies, and other rare medical conditions such as organ transplant recipients and systemic lupus erythematosus (Vail & Covington, 1997). Finally, idiopathic cases occur for a small proportion (<5%) of non-traumatic osteonecrosis.

In order to address the question of both sample size and heterogeneity of patients across the variety of osteonecrosis aetiologies, the proposed Phase III study has been designed to include a relatively homogeneous patient population, focusing on the most frequent aetiologies of the disease, *i.e.*, corticosteroid and alcohol associated osteonecrosis, as well as the idiopathic forms of osteonecrosis. It will therefore exclude others aetiologies such as trauma, sickle cell disease, other haemoglobinopathies, and dysbaric osteonecrosis.

Besides, it is interesting to note that, even if the exact pathophysiological mechanisms involved in osteonecrosis have yet to be fully elucidated, it is increasingly recognized that osteonecrosis of the femoral head is a disease of bone and/or MSCs (Hernigou & Beaujean, 1997; Gangji *et*

PREOB-ON3 - Clinical Study Protocol

PREOB-ON3-CSP	V 6.1	Author: [name]	May 15, 2017	Pg. 30/31
---------------	-------	----------------	--------------	-----------

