2.3.2 Inclusion and Exclusion Criteria

Inclusion criteria

To be eligible for the study, patients **must** satisfy **ALL** the following criteria:

1. Men or women between 18 and 70 years (inclusive) with a diagnosis of ARCO Stage I or II non-traumatic osteonecrosis of the femoral head, confirmed by central imaging analysis based on X-ray and MRI
2. Ability to provide a written, dated, and signed informed consent prior to any study related procedure and to understand and comply with study requirements
3. Diagnosis of osteonecrosis:
 - a. ARCO stage I associated with WOMAC® VA3.1 pain score ≥ 20 mm and necrotic angle sum $\geq 190^\circ$ based on sagittal and coronal MRI views

or

PREOB-ON3 - Clinical Study Protocol

PREOB-ON3-CSP | V 6.1 | Author: [name] | May 15, 2017 | Pg. 38/39

- b. ARCO stage II associated with WOMAC® VA3.1 pain score ≥ 20 mm if necrotic angle sum $< 190^\circ$ based on sagittal and coronal MRI views
 - or*
- c. ARCO stage II associated or not with pain if necrotic angle sum is $\geq 190^\circ$ based on sagittal and coronal MRI views
- d. Associated with corticosteroid and/or with alcohol abuse and/or idiopathic.

Table 1: Inclusion Criteria: Osteonecrosis Diagnosis

ARCO Stage	Necrotic Angles*	Pain**
Stage I	$\geq 190^\circ$	≥ 20 mm
Stage II	$< 190^\circ$	≥ 20 mm
Stage II	$\geq 190^\circ$	-

* Sum of coronal and sagittal necrotic angles

** WOMAC® VA3.1 pain during the 48 hours before screening

- 4. Normal haematology function, defined as leukocytes $\geq 3000/\text{mm}^3$, absolute neutrophils count $\geq 1500/\text{mm}^3$, platelets $\geq 140,000/\text{mm}^3$, and haemoglobin concentration $\geq 10\text{g/dl}$ (peripheral blood test)

Exclusion criteria

To be eligible for the study, patients **must NOT** present any of the following criteria:

Current symptoms and/or signs related to the disease under study

1. Exclusively diaphyseal or metaphyseal osteonecrotic lesion
2. Traumatic or hyperbaric osteonecrosis, or osteonecrosis associated with haemoglobinopathy or coagulopathy (e.g., thalassemia, sickle cell disease,...), or Gaucher's disease
3. Any other focal or diffuse bone marrow lesion
4. Osteoarthritis at the hip under evaluation defined as Kellgrens stage ≥ 2 , as assessed by the Central Radiologist
5. Patients suffering from any medical conditions interfering with patient's pain evaluation of the hip under evaluation, such as knee arthritis.

PREOB-ON3 - Clinical Study Protocol

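### The clinical responder rule is not monotone at a 10 mm baseline: for baselines of 10 to <14 mm, some scores inside the protocol's own no-pain range count as failure

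*Combined protocol and SAP*

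**What the plan says.** Section 10.1.1 splits the clinical half of the primary endpoint by baseline pain.

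- **Baseline 10 mm or more.** "For patients with a baseline WOMAC® VA3.1 pain subscale score ≥ 10 mm, the MCID can be used as a threshold value". These patients respond only if the "pain subscale score of the study treated hip decreased from baseline by at least the MCID". The size of the fall is fixed: "MCID value is set at 10 mm in accordance with the literature".
- **Baseline below 10 mm.** Here "the MCID cannot be used as a threshold value to define a clinically meaningful pain relief". These patients respond if the follow-up score lies between 0 and 4 mm inclusive. The protocol takes the range from a source "which states that any VAS pain rating ≤ 4 mm is labelled as" no pain.

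The same two branches appear in the synopsis and in sections 1.2, 2.2.1 and 10.1.2. None of these places lets a patient with a baseline of 10 mm or more qualify by ending in the no-pain range.

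On eligibility, section 2.3.2 and its Table 1 require a pain score of at least 20 mm for two of the three diagnostic routes. The third has no pain minimum: "ARCO stage II associated or not with pain if necrotic angle sum is" at or above 190°. Section 3.1 adds that when more than six weeks separate Visit 1b and Visit 2, the WOMAC is repeated and the new value becomes the baseline.

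**The concern.** A responder rule should not rank a patient who improves more and ends better below one who improves less and ends worse. This rule does so just above its own cut. A patient who goes from 9 to 4 mm falls by 5 mm and responds. A patient who goes from 10 to 1 mm falls by 9 mm, ends with less pain, is pain-free by the protocol's label, and is a clinical failure.

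Clinical response is a required half of the primary endpoint and is reused in the secondary treatment-responder and clinical-responder endpoints. What is at stake is the face validity of the endpoint in a narrow baseline band, and some true responses counted as failures, with a small loss of power.

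**Working it through.** **1. The rule, baseline by baseline.** Let b be the baseline and f the follow-up score, in mm. As written, response means f ≤ 4 when b < 10, and b − f ≥ 10 (that is, f ≤ b − 10) when b ≥ 10.

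| b | Highest f that responds | Fall needed | Whole-mm scores in 0-4 that fail |
|---|---|---|---|
| 9 | 4 | 5 | none |
| 10 | 0 | 10 | 1, 2, 3, 4 |
| 11 | 1 | 10 | 2, 3, 4 |
| 12 | 2 | 10 | 3, 4 |
| 13 | 3 | 10 | 4 |
| 14 | 4 | 10 | none |

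That is 4 + 3 + 2 + 1 = 10 whole-mm pairs that end in the no-pain range and fail. On a continuous scale the failing zone is b − 10 < f ≤ 4 for 10 ≤ b < 14. From 14 mm upwards any score of 4 mm or less is already a fall of at least 10 mm, so nothing is lost there. This assumes a subscale score on 0-100 mm, as the 10 mm and 4 mm limits imply; the WOMAC annex is not reproduced in the text.

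**2. Who can be in the band.** Two entry routes need 20 mm or more at screening. Baselines of 10 to <14 mm therefore come only from ARCO II with an angle sum of at least 190°, or from a repeat WOMAC that replaces the screening value. The documents give no baseline distribution.

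**3. The plan's sample size.** Inputs from section 10.4: 63% against 30%, two-sided 5%, chi-square. With pooled variance under the null,

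power = Φ{ [ |p1 − p2|·√n − z·√(2·p̄·(1 − p̄)) ] / √(p1(1 − p1) + p2(1 − p2)) }.

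At n = 46 per arm and z = 1.960 this is Φ{ (2.238 − 1.960 × 0.7054) / 0.6657 } = 0.901, which reproduces the stated 46 per arm at 90%. Also 1.19 × 92 = 109.5, rounded to 110. Sample size is not at fault.

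**4. Baseline power for the comparison.** Take 110/2 = 55 per arm and the nominal final level of section 10.7, 2 × 0.01341 = 0.02682 two-sided (z = 2.214): Φ{ (2.447 − 2.214 × 0.7054) / 0.6657 } = 0.908. This treats the final test alone and is approximate.

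**5. Size of the loss.** Let s be the share of patients in the band (assumed) and g the proportion of them whose response is lost. The observed rate is the planned rate minus s × g. The ceiling used here is that band patients would respond at the planned 63% and 30% and that all of those responses are lost.

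- s = 2% (118 × 0.02 ≈ 2 patients): PREOB 0.02 × 63 = 1.3 points; Placebo 0.02 × 30 = 0.6 points.
- s = 5% (118 × 0.05 ≈ 6 patients): PREOB 0.05 × 63 = 3.2 points; Placebo 0.05 × 30 = 1.5 points.

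| s | g (PREOB / Placebo) | Rates | Power, 55 per arm |
|---|---|---|---|
| 0 | - | 63.0% / 30.0% | 0.908 |
| 2% | 30% / 15% | 62.4% / 29.7% | 0.903 |
| 2% | 63% / 30% | 61.7% / 29.4% | 0.896 |
| 5% | 30% / 15% | 61.5% / 29.2% | 0.894 |
| 5% | 63% / 30% | 59.9% / 28.5% | 0.876 |

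**6. The proposed cut.** With f ≤ 4 required for b < 14 and b − f ≥ 10 for b ≥ 14, the highest responding score is 4 mm up to b = 14 and rises one for one after that, so it never drops as baseline rises. The change reclassifies exactly the ten whole-mm pairs in step 1. No current responder loses status: a fall of 10 mm from below 14 mm always ends below 4 mm.

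**The case against.** The strongest defence is that the rule is deliberate and worded consistently. Ten millimetres is the first baseline at which a 10 mm fall is arithmetically possible, so the MCID is used wherever it can be, and the no-pain range is a fallback where it cannot. On that view 13 to 4 mm fails because a 9 mm fall is below the MCID, and any two-branch dichotomy has a step. This explains why a cut was placed at 10 mm. It does not explain why 10 to 1 mm should rank below 9 to 4 mm. In the band a 10 mm fall can be reached only by ending below 4 mm, which is stricter than the protocol's own no-pain limit.

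Other parts of the defence stand. Few patients can be in the band. Absolute change in WOMAC pain is a secondary endpoint that needs no threshold. The fix credits falls below the MCID. Section 10 makes the SAP the main statistical reference; no separate SAP text is in the documents reviewed, so a handling rule or sensitivity analysis may exist there.

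A reader might infer more than the documents support:

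- **That each arm's rate could be understated by the whole 2-5 points.** This would need every patient in the band to be a radiological responder and to land in the narrow failing zone. The planned rates put the ceiling lower.
- **That the comparison is biased or type I error inflated.** The rule depends on baseline score and is identical in both blinded arms. If the product works, lost responses reduce power.
- **That this is a one-line edit.** It changes the primary endpoint wherever the definition is stated.

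**Conclusion.** The concern holds as a minor point of endpoint definition. For baselines of 10 to <14 mm, the rule counts as failures some patients whom the protocol itself would call pain-free, and it reverses the order of outcomes across the 10 mm cut.

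The effect is probably small. With an assumed 2-5% of patients in the band, the loss is at most about 1.3-3.2 points on PREOB and 0.6-1.5 points on Placebo, and power falls from about 0.91 to 0.90-0.88. These figures rest on the assumed share, and on the planned 63% and 30% describing what patients would achieve under a rule without the reversal. A larger share would cost more, and the documents do not allow the share to be estimated. There is no effect on type I error and no reason to change the sample size.

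**What to change.** Set the cut at 14 mm. With a baseline below 14 mm, the patient is a clinical responder if the score is between 0 and 4 mm inclusive. With a baseline of 14 mm or more, the patient is a responder if the score falls by at least 10 mm. An equivalent wording keeps the 10 mm cut and also accepts a score of 0-4 mm as response for baselines of 10 mm or more. Neither needs a new constant.

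Make the change in every place that states the definition (synopsis, sections 1.2, 2.2.1, 10.1.1 and 10.1.2) and in the SAP, so that the primary and secondary responder endpoints stay aligned. Decide it blinded and before any unblinded look at the interim analysis of section 10.7, which compares treatment responders. If that is no longer possible, keep the primary definition and pre-specify the 14 mm rule as a sensitivity analysis of the primary endpoint.

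The cost is a protocol amendment to the primary endpoint, with the authority and ethics approvals of section 11.9. In addition, falls of about 6-9 mm, below the MCID, will count as response in the 10 to <14 mm band when the patient ends in the no-pain range. The current rule already accepts falls of 5 mm at a baseline of 9 mm.

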10.1.2 Secondary Efficacy Endpoints

Efficacy will be assessed by the following secondary endpoints:

- Percentage of treatment responders at Month 6, 12 and 18, and over the 24-month follow-up period
- Percentage of clinical responders at Month 1, 3, 6, 12, 18 and 24, and over the 24-month follow-up period; a clinical responder being defined as a patient whom the WOMAC® VA3.1 pain subscale score of the study treated hip improved from baseline by at least the MCID^b at the studied timepoint
- Percentage of radiological responders at Month 6, 12, 18 and 24, and over the 24-month follow-up period; a radiological responder being defined as a patient whom the study treated hip did not progress to fractural stages (ARCO III or higher), as assessed by conventional X-ray, at the studied timepoint
- Absolute change from baseline in WOMAC® VA3.1 total score and composite pain, stiffness, and function subscale scores of the study treated hip at Month 1, 3, 6, 12, 18 and 24, and over the 24-month follow-up period
- Time to progression to fractural stages (ARCO III or higher) of the study treated hip
- Percentage of patients requiring hip arthroplasty for the study treated hip at Month 1, 3, 6, 12, 18 and 24, and over the 24-month follow-up period
- Time to hip arthroplasty for the study treated hip

^b The MCID value is set at 10 mm.

Patients with a baseline WOMAC® VA3.1 pain subscale score ≥ 10 mm will be considered, at the studied timepoint, as a clinical responder if the WOMAC® VA3.1 pain subscale score of the study treated hip decreased from baseline by at least the MCID.

Patients with a baseline WOMAC® VA3.1 pain subscale score < 10 mm will be considered, at the studied timepoint, as a clinical responder if the WOMAC® VA3.1 pain subscale score of the study treated hip is found in the range [0;4] (VAS pain range labelled as “no pain”).

PREOB-ON3 - Clinical Study Protocol

PREOB-ON3-CSP

V 6.1

Author: [name]

May 15, 2017

Pg. 85/86

10.2 Collection and Derivation of Safety Assessments

Safety will be assessed using the following variables:

- Adverse events (AEs) occurring throughout the study period
- Serious adverse events (SAEs) occurring throughout the study period
- Occurrence of any abnormality at physical examination at Month 1, 3, 6, 12, 18 and 24
- Vital signs (blood pressure, heart rate, body temperature and respiratory rate) evaluations and absolute change from baseline at Month 1, 3, 6, 12, 18 and 24
- Body Mass Index and absolute change from baseline at Month 1, 3, 6, 12, 18 and 24
- Hematologic and biochemical values and absolute change from baseline at Month 1, 3, 6, 12, 18 and 24
- Hematologic and biochemical values outside the normal ranges at Month 1, 3, 6, 12, 18 and 24
- Concomitant medications throughout the study period

